Rationale for between-subjects tDCS/Sham design: Our previous tDCS work suggests that, on average, participants in stimulation and sham conditions do report different kinds of sensations. To avoid cross-session learning effects, which would invalidate the sham condition, the experiments we propose here will manipulate tDCS between-subjects: Each participant will participate in an AM (8 or 9 AM) and PM (3 or 4 PM) testing session (within-subjects), and will be randomly assigned to the same tDCS condition in each session (left dlPFC or sham in older adults; left dlPFC, left parietal, or sham in younger adults), thereby avoiding any cross-session learning effects from experiencing different tDCS conditions.

Rationale for cognitive baseline measures: All participants will take a baseline version of the cognitive tasks (without tDCS) during the orientation session, serving as a no-tDCS baseline (i.e., the “pre” condition in a pre-post design). These cognitive baseline measures are included to assess Aim 3: Determine the extent that a pre-post between-subjects tDCS design can improve the detection of stimulation effects, while also preserving the validity of the sham condition. Our initial analyses will focus on the between-subjects comparisons described above, but the statistical power of the between-subjects design to detect group differences (stimulation vs sham) is likely limited by individual variability in task performance (unrelated to stimulation). In an attempt to reduce the contribution of individual variability that is unrelated to stimulation, and thereby provide a more sensitive test of tDCS effects, we will conduct additional analyses that include the baseline performance for all participants as a covariate. The primary purpose of this measure is to assess the value of a pre-tDCS baseline in detecting tDCS effects, independent from potential time of day effects explored in the other aims. Thus, to minimize time constraints on the completion of the project, these orientation

○

○

session testing times (and baseline cognitive assessment) will be scheduled at the convenience of the participant and experimenter (i.e., baseline sessions can occur outside the AM and PM testing windows that are reserved for the tDCS/sham sessions).

2 Sample Size and Randomization

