All analyses will initially be performed without using the baseline performance measures. We shall then repeat each analysis adjusting for the baseline value of the cognitive measure being analyzed. To the extent that the cognitive measures are highly correlated across timepoints, the latter analyses will provide additional power.

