### STATISTICAL SIGNIFICANCE

A two-sided p-value cutoff of 0.05 will be used for all null-hypothesis significance testing. In addition, point estimates for all first order and interaction effects will be reported, together with 95% confidence intervals. Between-individual contrasts (e.g., overall treatment effects) will be standardized (i.e., equivalent to Cohen’s d). Results of all analyses performed will be reported (not just those that meet the 0.05 cutoff). Since Hypotheses 1-4 are distinct, we shall not make any adjustment for multiple testing across the corresponding analyses. Within each analysis, we shall use a hierarchical approach in which we

begin with an overall test of the null hypothesis at the coarsest level, separately for episodic and working memory, and only if that is statistically significant will we conduct further testing among subgroups.

Although the primary analyses will utilize the frequentist approach to estimating and testing, we will complement this with a secondary Bayesian analysis using the same model. For parameters capturing treatment effects or between-group differences in treatment effects (i.e., interaction terms), we shall use a weakly informative prior (e.g.,  $\text{Normal}(0, 1-10)$ ). The primary value of this analysis will be to provide more interpretable (i.e., probability) statements about the magnitude of the effects of tDCS and about the amount of information contained in the data.

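### The SAP tests each primary hypothesis without and then with baseline adjustment, both at .05, and does not say which result decides or opens the gate to further testing

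*SAP*

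**What the plan says.** The SAP's Primary Analyses section sets the order: "All analyses will initially be performed without using the baseline performance measures", followed by "We shall then repeat each analysis adjusting for the baseline value of the cognitive measure being analyzed". It gives the reason for the second pass: "To the extent that the cognitive measures are highly correlated across timepoints, the latter analyses will provide additional power".

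The SAP's Statistical Significance section then says: "A two-sided p-value cutoff of 0.05 will be used for all null-hypothesis significance testing". Its multiplicity statement concerns different hypotheses: "Since Hypotheses 1-4 are distinct, we shall not make any adjustment for multiple testing across the corresponding analyses". Its hierarchy works within an analysis: the team will "begin with an overall test of the null hypothesis at the coarsest level, separately for episodic and working memory", and goes on to subgroups only if that test is significant. Neither rule mentions the pair formed by the unadjusted and adjusted versions of the same test.

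The protocol does rank the two. Section 9.1 gives the initial focus to the unadjusted between-subjects comparisons and continues: "we will conduct additional analyses that include the baseline performance for all participants as a covariate". Section 3 lists the within-subjects baseline among secondary analyses, and section 1.2 puts the value of the baseline under secondary objectives. Section 9.1 also says that person-to-person variability probably limits the unadjusted comparison, and that the baseline is meant to give a more sensitive test. The baseline tasks are given to every participant.

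**The concern.** A reader of the SAP will have two p-values for each primary hypothesis and no statement of which one answers it. This also affects what is tested next. Subgroup testing depends on a significant overall test, but there are two overall tests and neither is named as the one that opens the gate.

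What is at stake depends on how the gap is filled. If the unadjusted version decides, as the protocol's labels suggest, the trial rests its conclusion on the test its authors expect to be less sensitive, while holding a baseline score on everyone. If either version may count, each hypothesis gets two attempts at .05.

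**Working it through.** **Inputs.** From the protocol's power analysis (section 9): sham mean .23, active mean .35, SD .21, 50 per group, two-sided .05, target power 80%, and a correlation of .25 between the AM and PM measures. The correlation r between baseline and a session score is not in the documents. I assume .25, .50 and .60.

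**1. The plan's own figure.** d = (.35 − .23)/.21 = .571, which the protocol gives as .57. The noncentrality is d·√(n/2) = .57 × √25 = 2.85 on 98 degrees of freedom, so power is 80.6% (80.8% with d = .571). Fifty per group is the smallest number that reaches 80%. The stated sample size reproduces, as an unadjusted comparison.

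**2. Power if the adjusted test decides.** Adjustment reduces the residual SD to .21·√(1 − r²), so the effective d is .57/√(1 − r²) and the noncentrality is 5 times that, on 97 degrees of freedom.

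| r (assumed) | √(1 − r²) | Effective d | Noncentrality | Power | Gain over 80.6% |
|---|---|---|---|---|---|
| .25 | .968 | .589 | 2.94 | 83.0% | 2.4 points |
| .50 | .866 | .658 | 3.29 | 90.3% | 9.7 points |
| .60 | .800 | .713 | 3.56 | 94.1% | 13.5 points |

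By the normal approximation, the number per group for 80% power is 49 unadjusted and 46, 37 and 31 adjusted.

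**3. Error rate if either test may count.** Under the null, the unadjusted and adjusted statistics have correlation √(1 − r²). The chance of at least one false positive is 1 − P(|Z₁| < 1.96 and |Z₂| < 1.96) for a bivariate normal with that correlation.

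| r (assumed) | Single session | AM/PM mean |
|---|---|---|
| .25 | 6.2% | 6.5% |
| .50 | 7.3% | 7.7% |
| .60 | 7.8% | 8.1% |

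For the AM/PM mean, the correlation with baseline is r/√((1 + r)/2) = .316, .577 and .671, which assumes the same r between all three sessions. Simulated null trials with 50 per arm agree: 6.1% and 7.1% for a single session at r = .25 and .50, and 6.4%, 7.7% and 8.0% for the mean. Two independent tests would give 1 − .95² = 9.75%. The pair stays below that because the two tests are strongly correlated.

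**4. Which contrasts are affected.** The baseline score takes one value per person. If it enters the model as a covariate with coefficient β, it adds the same β × baseline to that person's AM and PM scores, and the term cancels in the AM − PM difference. Protocol section 5.4 limits the primary analyses to people who complete all three sessions, so the stimulation by time-of-day interaction is estimated from such differences. Adjustment leaves its power essentially unchanged, and the two versions of its test are nearly identical. The figures in steps 2 and 3 therefore apply to stimulation and to stimulation by age group.

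**The case against.** The strongest reply is that leading with the unadjusted model is a deliberate and defensible choice. The sample size was set for that contrast and gives its 80% power. The first objective is to replicate earlier findings. Aim 3 asks whether a baseline helps, so both versions must be run. Protocol section 9.1 already ranks them, and the SAP undertakes to report every analysis whether or not it is significant.

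Much of this stands, and it rules out several stronger readings that a reader might infer:

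- **That no document ranks the two versions.** Only the SAP is silent; protocol sections 1.2, 3 and 9.1 are not. Section 3 is weak evidence for the SAP's order, because it also calls the sleep and parietal analyses secondary while the SAP lists them as primary. Section 9.1 is directly on point.
- **That power is lost and error is inflated together.** These are alternatives. If the unadjusted test alone decides, its error rate is 5%. If either may count, the more powerful test is available.
- **That every hypothesis is affected.** Step 4 of the working excludes the stimulation by time-of-day interaction.
- **That the loss is known to be large.** At .25, the only between-session correlation stated, it is about 2 points. Baseline sessions are held at varying times of day, which may lower the correlation. The higher values are assumptions, and applying them to all three sessions departs from the stated AM–PM value of .25. The single-session error rates do not need that step.

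The power figures also use the protocol's AM sizing scenario, which is not itself a listed SAP analysis. Even so, full reporting does not say which p-value answers the hypothesis or opens the gate, and Aim 3 does not require the less sensitive test to lead.

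**Conclusion.** The point holds as a gap in the SAP with a modest and uncertain cost. The SAP does not settle which version of each primary test decides, or which overall test permits subgroup testing. If the unadjusted version decides, between-person contrasts have 81% power where adjustment would give 83% to 94%, for d = .57, 50 per arm and an assumed baseline correlation of .25 to .60. If either may count, the error rate per between-person hypothesis is about 6% to 8%. The documents do not support a claim that the trial is underpowered on its own terms, since its stated sample size reproduces. The change is still worth making: it uses a score already collected on everyone and follows the reasoning that both documents give.

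**What to change.** Before the stimulation codes are broken, state in the SAP that the baseline-adjusted model is the decisive analysis for each primary hypothesis and is the overall test that opens the hierarchical gate. Report the unadjusted model beside it, with estimates, standard errors and the ratio of the standard errors, for Aim 3 and for comparison with the earlier study. Make no separate significance claim from it. Align the wording of protocol sections 1.2, 3 and 9.1.

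No new data or models are needed. The cost is a small protocol wording amendment alongside the SAP change. The decisive test will also no longer match the unadjusted contrast used for the sample size, although that result will still be reported.

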### STATISTICAL SIGNIFICANCE

A two-sided p-value cutoff of 0.05 will be used for all null-hypothesis significance testing. In addition, point estimates for all first order and interaction effects will be reported, together with 95% confidence intervals. Between-individual contrasts (e.g., overall treatment effects) will be standardized (i.e., equivalent to Cohen’s d). Results of all analyses performed will be reported (not just those that meet the 0.05 cutoff). Since Hypotheses 1-4 are distinct, we shall not make any adjustment for multiple testing across the corresponding analyses. Within each analysis, we shall use a hierarchical approach in which we

begin with an overall test of the null hypothesis at the coarsest level, separately for episodic and working memory, and only if that is statistically significant will we conduct further testing among subgroups.

Although the primary analyses will utilize the frequentist approach to estimating and testing, we will complement this with a secondary Bayesian analysis using the same model. For parameters capturing treatment effects or between-group differences in treatment effects (i.e., interaction terms), we shall use a weakly informative prior (e.g.,  $\text{Normal}(0, 1-10)$ ). The primary value of this analysis will be to provide more interpretable (i.e., probability) statements about the magnitude of the effects of tDCS and about the amount of information contained in the data.
